### 1.2 Specific Aim 2. Secondary Outcomes--Stroke Education and Prevention:

Many patients with stroke know little about the causes of their condition and consequently have poor control of stroke-related risk factors. Improving patient knowledge about stroke can therefore help to prevent stroke recurrence and to optimize patient outcomes. While all certified stroke centers include patient education as a priority during the acute stroke admission, patients and their families may not be in the best position to benefit from such education at this time as compared to once they have returned to their home. Aim 2 will compare two different approaches to patient education in their impact on stroke knowledge, hypothesizing that both are effective, and are effective to an equal extent. As an extension of this issue, the degree of gains in stroke knowledge is hypothesized to be related to the extent to which patients implement appropriate lifestyle changes.

**1.2.1** Subjects, having received targeted educational material for 6 weeks, will significantly increase knowledge related to stroke prevention and stroke risk factor control, measured as the change in percentage of questions answered correctly on the Stroke Education Exam from Screening Visit to Post-Therapy Visit.

**1.2.2** The change in percentage of questions answered correctly on the Stroke Education Exam from Screening Visit to Post-Therapy Visit among subjects using the telerehabilitation system will be comparable to the change in percentage of questions answered correctly on the Stroke Education Exam among subjects using a traditional paper booklet-based method.

**B.1.3** Increased stroke knowledge will be positively correlated with improvement in weight and blood pressure control.

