## 8. STATISTICAL CONSIDERATIONS, DATA ANALYSIS AND DATA MONITORING

In the study, populations used for testing comparable efficacy, the non-inferiority margin proposed for determining comparable efficacy, the statistical procedures used for summarizing and testing the primary and secondary comparable efficacy endpoints, and sample size justification for the proposed study. All analyses are two-tailed and use  $\alpha=0.05$ .

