**8.5 Secondary outcome measures:****Stroke education**

- Gains in stroke knowledge from Screening Visit to Post-Therapy Visit, measured as the change in percentage of questions answered correctly on the Stroke Education Exam

In order to determine whether targeted educational material significantly increases subject knowledge related to stroke, the Stroke Knowledge Exam will be administered twice, once at the Screening Visit then again at the Post-Therapy Visit. A repeated measures ANOVA will be performed to determine if the percentage of Stroke Knowledge Exam answered correctly increases significantly from the Screening Visit to the Post Therapy Visit, controlling for days from stroke onset to randomization, initial Stroke Knowledge Exam score (at the Screening Visit), age, and enrollment site. To determine if gains in stroke knowledge vary according to the method by which stroke education is delivered, analysis will be repeated adding a time X group interaction term. Weight and blood pressure will be measured during the Screening Visit as well as during the Post Therapy Visit. In order to determine whether gains in stroke knowledge are associated with improvements in stroke risk factor control, the relationship between gains in stroke knowledge (the change in percentage of questions answered correctly on the Stroke Education Exam from the Screening Visit to the Post Therapy Visit) and improvement in weight and blood pressure control (change in weight, change in systolic blood pressure, and change in diastolic blood pressure) will be examined, controlling for days from stroke onset to randomization, Stroke Knowledge Exam score at Screening Visit, age, and enrollment site, and using a Bonferroni-adjusted alpha = 0.017; again, analyses will be repeated by adding a time X group interaction term.

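### The repeat of the knowledge versus weight and blood-pressure analyses adds a time X group term, which is undefined in the model described and cannot compare the association between education methods

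*Combined protocol and SAP*

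**What the plan says.** Section 8.5 (Stroke education) sets out two analyses.

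- **Exam scores.** A repeated measures ANOVA compares the Stroke Knowledge Exam at Screening and Post-Therapy. It is then rerun with a time X group term, for the stated purpose of seeing whether knowledge gains depend on how the education is delivered.
- **Association with risk factors.** The predictor is "the change in percentage of questions answered correctly on the Stroke Education Exam from the Screening Visit to the Post Therapy Visit". The outcomes are "change in weight, change in systolic blood pressure, and change in diastolic blood pressure". The adjustment is given as "controlling for days from stroke onset to randomization, Stroke Knowledge Exam score at Screening Visit, age, and enrollment site", and the tests are done "using a Bonferroni-adjusted alpha = 0.017". The sentence ends: "again, analyses will be repeated by adding a time X group interaction term".

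The second analysis serves item B.1.3 of Aim 2 (Section 1.2): "Increased stroke knowledge will be positively correlated with improvement in weight and blood pressure control". That item is a single overall correlation. It states no hypothesis about a difference between arms.

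**The concern.** In the exam-score analysis time is a factor with two levels, so time X group is the right term for comparing gains between arms. In the association analysis each subject contributes one predictor value and one outcome value, both already differenced over time. There is no time factor for group to interact with.

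The analyst would therefore have to choose a model after the fact. If the repeat is meant to ask whether knowledge gain tracks risk-factor change differently under the two education methods, the named term does not address that question under any two-visit model. It could be non-significant when the associations differ, and significant when only the mean changes differ. No interaction between knowledge gain and group is specified anywhere in the plan.

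**Working it through.** **Inputs.** Overall alpha is 0.05, two-sided (Section 8: "All analyses are two-tailed and use" 0.05). There are three outcomes at an adjusted alpha of 0.017 (Section 8.5). The illustration uses 62 subjects per arm, from the sample size paragraph of Section 8.3. All correlations and mean differences below are assumptions, in SD units; the documents give none.

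**The plan's own figure.** 0.05/3 = 0.0167, which rounds to the stated 0.017. It is reproduced, and it covers the three association tests.

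**What each term estimates.** Let dK be knowledge gain, dY the change in weight or blood pressure, G the arm, and Z the listed covariates.

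1. As described: dY = b0 + b1·dK + c·Z + error, one row per subject. Time does not appear, so time X group cannot be formed.
2. Recast with Y at two visits, including time and time X group: subtracting the visits gives dY = a + d·G + error. The coefficient d is the arm difference in mean change.
3. As 2, with time X dK also included: dY = a + b1·dK + d·G + error. Now d is the arm difference in mean change adjusted for knowledge gain. One slope b1 is forced on both arms.
4. To let the association differ by arm: dY = b0 + b1·dK + b2·G + b3·(dK·G) + error. The slopes are b1 and b1 + b3, and b3 is their difference. In two-visit form, b3 is the coefficient of time X group X dK.

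Only model 4 contains a parameter for a difference in association. Section 8.5 and the Data Collection Schedule differ on when the second weight and blood-pressure reading is taken. That is a separate matter: there are two readings either way, so this algebra holds.

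**Simulation with differing associations.** Standardised change scores, 62 per arm, two-sided alpha 0.017, correlation 0 in one arm and r in the other, equal mean changes.

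| r | gain X group rejects | time X group rejects |
|---|---|---|
| 0.2 | about 10% | about 2% |
| 0.3 | about 23% | about 2% |
| 0.4 | about 45% | about 2% |
| 0.5 | about 68% | about 2% |

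Hand check at r = 0.4: the standard error of the slope difference is about √[(1 + (1 − 0.4²))/62] = √(1.84/62) = 0.172. Then 0.4/0.172 = 2.32. The critical value for two-sided 0.017 is 2.387, so power is about Φ(2.32 − 2.387) = Φ(−0.07), or 47%. This agrees with the simulated 45%.

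**Simulation in the other direction.** With equal slopes of 0.3 and mean change differing by 0.6 SD between arms (2,000 runs, residual SD 1), time X group rejects in 79.9% of runs without knowledge gain in the model and 83.4% with it. Gain X group rejects in 1.8%, close to nominal.

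**The case against.** Four points can be made for the plan.

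- **The purpose is not stated.** The repeat might ask the parallel question, whether weight and blood-pressure change differ by method, and time X group answers that. This stands. That the repeat is meant to compare the association rests on the word again and on the sentence's subject: "In order to determine whether gains in stroke knowledge are associated with improvements in stroke risk factor control, the relationship between gains in stroke knowledge".
- **No model is named.** The plan says only that the relationship will be examined. In a two-visit model containing knowledge gain X time, adding time X group is estimable and adjusts the association for arm, which the listed covariates do not. The adjustment can matter. With no association within arms and arms differing by an assumed 0.8 SD in both gain and blood-pressure change, the unadjusted association rejects in 19% of runs at 0.017, against 1.7% with the arm term. This also stands, and it is why the claim is limited to the model as described.
- **The 2% is true by construction.** Mean changes were set equal, so a test of mean change must reject at its alpha. That is correct. The figure shows that the term is silent on the association; it does not measure harm.
- **The replacement has low power for modest differences.** At r = 0.3 it misses about 77% of trials. This stands and belongs in the plan's wording.

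A reader might go further and infer that the term can never be fitted, that real differences in association will be lost because of it, or that analysts will misread an arm difference as a different link. The documents support none of these. A repeated-measures recast makes the term estimable, the correct term would also miss most modest differences, and Section 8.5 proposes no such interpretation.

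**Conclusion.** The point holds in a limited form. As described, the association analyses have no time factor, so the added term is undefined. Under a two-visit recast it concerns the arm difference in mean change and never a difference in the knowledge slope. The algebra shows this without any assumption about effect size. The detection rates in the table depend on assumed correlations and on 62 analysable subjects per arm.

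Two things remain conditional. That the repeat is intended to compare the association between methods is inferred. The practical loss is also small unless the associations differ a good deal.

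Severity is minor. This is a supplementary repeat under a secondary aim, with no between-arm hypothesis in item B.1.3. The main B.1.3 correlation, the primary endpoint and the sample size are untouched, and the exam-score use of time X group is correct.

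**What to change.** Amend the closing clause of the stroke education paragraph in Section 8.5:

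- State the model and the purpose of the repeat.
- In the three B.1.3 models, replace time X group with treatment group plus knowledge gain X treatment group. If a repeated-measures model is kept, use time X group X knowledge gain with its lower-order terms.
- Report the slope in each arm with its confidence interval, labelled supplementary, and note the low power for modest differences.
- State that the three interaction tests form their own family at 0.05/3 = 0.017, separate from the three association tests.
- Keep time X group for the exam-score analysis.

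If the sponsor instead wants the arm difference in mean weight or blood-pressure change, or an arm-adjusted association, the text should say so. The cost is a sentence or two in Section 8.5, with no new data or visits.

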**Compliance and motivation.**

- Compliance with therapy, defined as the percentage of the 36 therapy sessions for which the subject completed assigned activities for at least 40 minutes

Compliance with rehabilitation therapy will be examined across all 36 sessions. For supervised sessions, a subject will be considered compliant if at least 40 min of assigned

therapy has been completed, determined from the therapist notes for subjects in the in-clinic group and from telerehabilitation system usage data for subjects in the telerehabilitation group. For unsupervised sessions, a subject will be considered compliant if at least 40 min of assigned therapy has been completed based on self-report for the in-clinic group and by telerehabilitation system usage data for subjects in the telerehabilitation group. To determine whether compliance with therapy differs according to treatment group, ANCOVA modeling will be used to examine compliance across the 36 sessions as a function of treatment group, controlling for days from stroke onset to randomization, age, and enrollment site. Secondary analysis will examine compliance with only the supervised therapy sessions, as well as compliance with only the unsupervised sessions.

**Motivation** (assessed along two independent dimensions):

- Activity-inherent motivation, defined as the change in score on the Physical Activity Enjoyment (PACES) Scale from baseline to end of the first week of therapy
- Consequence-related motivation, defined as the score on the Optimization in Primary and Secondary Control (OPS) Scale at the Baseline Visit

Activity-inherent motivation reflects how much a subject likes or dislikes an activity itself, independent of his or her commitment to the treatment goals. To measure this, the PACES Scale will be scored three times (at the Baseline Visit, after 3 supervised sessions, and after 18 supervised sessions). Activity-inherent motivation will be defined as the change in PACES score. Primary analysis will examine the change from baseline to end of week 1, while secondary analysis will examine change from baseline to end of week 6. To determine whether activity-inherent motivation is different for in-clinic vs. telerehabilitation therapy, ANCOVA modeling will examine differential change in PACES score between the two treatment groups, controlling for days from stroke onset to randomization, PACES score at the Baseline Visit, age, and enrollment site.

Consequence-related motivation reflects a subject's level of commitment to treatment goals. To measure this, the OPS Scale will be scored three times (at the Baseline Visit, after 3 supervised sessions, and after 18 supervised sessions). We hypothesize that across both treatment groups, the baseline level of consequence-related motivation (OPS score at the Baseline Visit) will predict compliance with rehabilitation therapy. Furthermore, we hypothesize that when consequence-related motivation is high compliance will be high for both treatment groups, however when consequence-related motivation is low compliance may be lower overall but will vary with the level of activity-inherent motivation. ANCOVA modeling will be used to determine if consequence-related motivation is a significant predictor of compliance with therapy (as defined above, across all 36 sessions), controlling for days from stroke onset to randomization, age, and enrollment site. Primary analysis will define consequence-related motivation using the OPS subscale that measures selective primary and selective secondary control striving (also referred to as goal engagement). Secondary analyses will define consequence-related motivation using the entire OPS score, and will also examine the effect of treatment group. An additional analysis will examine add the interaction term OPS x PACES to determine whether compliance varies with consequence-related motivation in a manner that depends on level of activity-inherent motivation; PACES and OPS scores will be centered and then combined in the interaction term.

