### 1.3 Specific Aim 3. Patient Compliance with and Motivation for Therapy:

A major issue in rehabilitation therapy is patient compliance. Compliance and its variance across patients will be examined by measuring two dimensions of motivation. Aim 3 hypothesizes that compliance and activity-inherent motivation will be comparable across the two study treatment groups, and that compliance will vary with consequence-related motivation.

**1.3.1** Compliance with therapy, defined as the percentage of the 36 therapy sessions for which the subject completed assigned activities for at least 40 minutes, will be comparable or better with telerehabilitation as compared to compliance with in-clinic therapy.

**1.3.2** Activity-inherent motivation, which reflects how much a patient enjoys a therapy and defined as the change in score on the Physical Activity Enjoyment (PACES) Scale

from the Baseline Visit to end of the first week of therapy, will be at least as high (and in many patients higher) with telerehabilitation as compared to in-clinic therapy.

**1.33** Level of consequence-related motivation, which reflects the patient's degree of dedication to treatment goals and defined as the score on the Optimization in Primary and Secondary Control (OPS) Scale at the Baseline Visit, will emerge as a significant predictor of compliance in both groups, even after controlling for key variables. When consequence-related motivation is high, compliance will be high, for both treatment groups. When consequence-related motivation is low, compliance may be lower but will vary with the level of activity-inherent motivation.

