## **5. EXPERIMENTAL DESIGN AND METHODS**

### **5. 1. Methods and Procedures**

The current study will test the effectiveness of a novel home-based telehealth system designed to improve motor recovery and patient education after stroke. A total of 124 subjects with arm motor deficits 4-36 weeks after a stroke due to ischemia or to intracerebral hemorrhage will be randomized to receive 6 weeks of intensive arm motor therapy (a) in a traditional in-clinic setting –Standard therapy arm or (b) via in-home telerehabilitation (rehabilitation services delivered to the subject’s home via an internet-connected computer) - Investigational arm. The intensity, duration, and frequency of this therapy will be identical across the two groups, with subjects in both treatment arms receiving 36 sessions (18 supervised and 18 unsupervised), 80 minutes each (including a 10 minute break), over 6 weeks. Arm motor status is the focus here because it is commonly affected by stroke, is of central importance to many human functions, and is strongly linked to disability and well being after stroke.

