**Stroke education:**

At the start of each of the 18 unsupervised sessions, all subjects will receive 5 minutes of stroke education. The information presented corresponds to the content of the Stroke Knowledge Exam, which focuses on prevention, recognition, response, and management of stroke. Subjects assigned to in-clinic therapy will review the stroke education booklet. Subject assigned to telerehabilitation will receive this information via the telerehab system.

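### The 40-minute rule scores 57% of a session's active time as full compliance, so a between-arm gap in therapy time above that level cannot be seen

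*Combined protocol and SAP*

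**What the plan says.** Section 8.5 (Compliance and motivation) takes compliance with therapy, "defined as the percentage of the 36 therapy sessions for which the subject completed assigned activities for at least 40 minutes". Section 1.3.1 uses the same definition and expects that compliance "will be comparable or better with telerehabilitation as compared to compliance with in-clinic therapy"; it gives no margin for this comparison.

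The score is the outcome in two models in Section 8.5. For the arms, "ANCOVA modeling will be used to examine compliance across the 36 sessions as a function of treatment group". For motivation, "ANCOVA modeling will be used to determine if consequence-related motivation is a significant predictor of compliance with therapy". The only further compliance analyses split supervised from unsupervised sessions under the same rule.

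Section 5.1 sets the assigned dose at "36 sessions (18 supervised and 18 unsupervised), 80 minutes each (including a 10 minute break), over 6 weeks" and says that intensity, duration and frequency are the same in both groups. Section 5.3.3 says they will be carefully matched.

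The source of the data differs by arm. In supervised sessions it is therapist notes (in-clinic) or system usage data (telerehabilitation). In unsupervised sessions compliance is judged "based on self-report for the in-clinic group and by telerehabilitation system usage data for subjects in the telerehabilitation group".

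Section 8.1 uses the same cut for the Per-Protocol Population: at least 40 minutes at 15 or more of the 18 supervised sessions. No section gives a reason for 40 minutes or plans an analysis of minutes completed.

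**The concern.** Every session from 40 to 70 active minutes gets the same score. If one arm tends to stop early but after minute 40, the planned comparison cannot detect it. Section 2.1 argues that the amount and duration of therapy drive outcome, so therapy time is what a reader of a non-inferiority result will want to see matched.

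The design makes unequal shortening plausible. In-clinic supervised sessions have a therapist present for the full 80 minutes (Section 5.3.3.1). In telerehabilitation the therapist disconnects after 30 minutes and the subject continues alone for 50, break included (Section 5.3.3.2). If those first 30 minutes count in full, 10 more reach the cut, and the last 30 active minutes (70 - 40) do not affect the score.

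Aim 3 hopes to find the arms comparable, so a measure that hides differences works in favour of the hypothesis. If most subjects score at or near 100%, the OPS model also has little variation to explain.

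**Working it through.** **1. Dose hidden by the cut (documents only).**
- Active minutes per session: 80 - 10 = 70.
- Lowest time that scores as compliant: 40/70 = 57.1%.
- Over the course: 36 x 40 = 1,440 of 36 x 70 = 2,520 minutes scores 100%.
- Largest invisible gap: 1 - 0.571 = 42.9%, or 1,080 minutes.
- Sensitivity: counting the break, 40/80 = 50%. If the 5 minutes of education in unsupervised sessions lie inside the 80 and do not count, 40/65 = 61.5%. The documents do not settle this.
- The per-protocol rule does not close the gap: 15 x 40 = 600 of 18 x 70 = 1,260 supervised active minutes (48%) is enough to qualify.

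**2. The plan's own figures.** The documents give no power, SD or effect size for compliance. N=124 comes from the Fugl-Meyer endpoint. With margin 2.05, SD 4.0, one-sided 0.025, 80% power and a true difference of zero (not stated in the sample-size text), it reproduces closely: 60 per arm by the normal formula and 61 by noncentral t, against 62 stated. The pilot figure is 329/336 = 97.9% of assigned days.

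**3. Effect on power (assumed distributions).** Each case is a simulation with 62 per arm, 36 sessions, a linear model with arm and standardised OPS, two-sided 0.05 and 3,000 runs. The planned covariates are left out. Partial-session cases assume a 3.5-minute arm difference, 2 minutes per SD of OPS, between-subject SD 6 and within-subject SD 8. The mixed case uses smaller effects on minutes plus an effect on skipping.

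| How subjects fall short | Arm: cut vs minutes | OPS: cut vs minutes |
|---|---|---|
| Sessions done in full or skipped | 58% vs 58% | 67% vs 67% |
| Effects on skipping only; attended minutes vary for unrelated reasons | 58% vs 37% | 65% vs 45% |
| Skipped and shortened | 65% vs 77% | 75% vs 87% |
| Shortened only, mean about 60 min | 45% vs 87% | 57% vs 94% |
| Shortened only, mean about 50 min | 77% vs 89% | 84% vs 94% |
| Shortened only, mean about 42 min | 84% vs 88% | 91% vs 94% |

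For arms, the cut runs from 45 - 87 = -42 points to 58 - 37 = +21 points relative to minutes. In the 60-minute case, 74% of subjects score exactly 100%.

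**4. Which minutes can be compared between arms.** With no true arm difference and in-clinic subjects over-reporting unsupervised minutes by 5 to 10 (assumed), false positives were 35-98% on minutes over all 36 sessions and 12-38% on the cut. On supervised-session minutes they stayed at about 5%. With a true 4-minute difference (mean 62, SD 8, assumed), arm power was about 74% on supervised minutes and about 41% on the cut.

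**The case against.** The case for leaving the outcome alone has real force.

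- **The score is not a yes/no per subject.** It is a percentage in steps of 1/36, and it captures missed sessions fully. Information is lost only on minutes within attended sessions, which the documents do not describe. This stands.
- **A reader might infer that power necessarily falls.** The documents do not support that. Step 3 shows a large loss, no loss, or an advantage for the cut, depending on how subjects fall short.
- **A reader might take the pilot's 97.9% as proof of a ceiling.** It counts days engaged, not sessions of at least 40 minutes, in 12 telerehabilitation subjects over 28 days with no comparison arm. It makes a ceiling plausible and no more.
- **A reader might conclude that total minutes should replace the outcome.** Half of the in-clinic sessions rest on self-report, and Section 3 reports that pilot subjects' recall of their usage was not significantly related to actual values. Logged minutes on one side and reported minutes on the other would bias the arm comparison. The 40-minute answer rests on the same self-report but was less sensitive to over-reporting in step 4. This stands, and it rules out all-session minutes as the between-arm test.
- **The contrast of 40 against 70 minutes in every session is extreme,** given the therapist's presence in clinic. It marks the limit of what the rule can hide and is not a forecast.

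None of this answers the main point: a shortfall above 40 minutes is invisible in every planned analysis. Supervised sessions do not depend on self-report in either arm.

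**Conclusion.** The point holds. By the documents' own figures, 57% of active time scores as full compliance and a between-arm gap of up to 43% is hidden, while the plan describes duration as matched. A finding of comparable compliance would not show comparable therapy time.

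The effect on power is conditional. It can be large if subjects shorten sessions that still pass 40 minutes. It is absent, or favours the cut, if non-compliance is mainly skipped sessions. All the power and false-positive figures rest on assumed distributions of minutes and assumed over-reporting.

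Compliance is a secondary outcome. The Fugl-Meyer analysis and N=124 are unaffected.

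**What to change.** Keep the percentage of the 36 sessions of at least 40 minutes as the stated compliance outcome; it then stays in line with the per-protocol rule. Add to Section 8.5:

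- A pre-specified ANCOVA of the percentage of assigned active minutes completed in the 18 supervised sessions. Cap minutes at the assigned active time, enter 0 for a session not done, sum, and divide by 18 times the assigned active time. Take minutes from therapist notes and system usage data, with active time defined alike in both arms. Use it for the arm comparison and for the OPS model, with the covariates already named for compliance.
- A statement that this result is reported beside the 40-minute result before compliance is called comparable.
- A descriptive summary, by arm, of minutes over all 36 sessions, with no between-arm test because the unsupervised data sources differ.

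The cost is protocol and SAP wording, entry of minutes for supervised sessions on the existing Therapy Compliance form, and one more secondary analysis. No new visit, device or staff is needed.
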